## COVARIATE ANALYSIS

The impact of the following potential covariates on study outcome will be evaluated:

- Baseline VAS rating
- Age
- Gender
- Ethnicity
- Etiology

Analysis of results will be performed by individual test site and pooled across test sites.

## SAFETY ANALYSES

Safety analyses will be based on all enrolled subjects and will be assessed by evaluating and comparing frequency and incidence of observed and/or reported adverse events between dual-diode and red diode only procedure groups. A chi-square test with a continuity correction will be performed to compare the percentage of subjects who had adverse events between the two subject groups.

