## **PROCEDURE ADMINISTRATION PHASE**

### **PROCEDURE ADMINISTRATION PROTOCOL**

- The procedure administration phase of the study directly follows successful completion of the pre-procedure evaluations phase, on the same day.
- The procedure administration phase comprises a single procedure administration with the Erchonia® EVRL.
- The procedure administration lasts a total of 13 minutes.
- The procedure administration with the Erchonia® EVRL is administered at the test site.
- The procedure administration protocol is identical to that in the retrospective control study, and is as follows:
  1. The subject enters the procedure room and is seated comfortably.
  2. The subject is correctly fitted with the protective eyewear.
  3. The Erchonia® EVRL is positioned and centered 6 inches above the subject's sagittal suture (top of the head).
  4. One minute of pulsed laser is applied to the sagittal suture (top of the head).
  5. Two minutes of pulsed laser is then applied to the left cervical, shoulder and torso area. The laser is applied starting in the cerebral region, at the top of the ear, lasering left cervical anterior and posterior muscles, working the laser down into the left shoulder and torso anterior and posterior muscles.
  6. Step 5 is repeated to the subject's right cervical shoulder and torso area.
  7. One minute of pulsed laser is then applied to right shoulder during passive external rotation of the shoulder. The anterior muscles of the right shoulder (pectoralis group) are lasered, with the subject's arm bent at the elbow.
  8. One minute of pulsed laser is then applied to the right shoulder during passive adduction of the subject's right arm and shoulder. The posterior muscles of the right shoulder are lasered.
  9. One minute of pulsed laser is then applied to the right cervical muscle and trapezius muscle during passive left lateral flexion of the cervical spine. Starting in the neutral position of the head, the laser light is applied to the right cervical muscles and right trapezius muscles.
  10. One minute of pulsed laser is then applied to the right sternocleidomastoid and scalene muscles during passive range of motion. The laser light is applied to the right sternocleidomastoid and scalenus muscles.
  11. Step 7 is then repeated to the left shoulder.
  12. Step 8 is then repeated to the left shoulder.
  13. Step 9 is then repeated to the left cervical spine.

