## **ADVERSE EVENTS**

At each evaluation point throughout the clinical study, and at any other time throughout the duration of the clinical trial that is necessary, any and all potential adverse events reported by a subject or observed by an investigator will be recorded on the case report form, and subsequently evaluated by a suitably qualified independent reviewer for determination of relationship to the study treatment and whether or not any corrective action needs to be taken. All potential adverse events recorded will be appropriately reported to the governing IRB, as applicable.

It is unlikely and not expected that any adverse events will result from implementation of this clinical study protocol. Prior clinical trials using low level laser light have not typically yielded any adverse events or reactions. However, potential adverse events that may feasibly occur from application of the Erchonia® EVRL include, but are not necessarily limited to: skin irritation, discoloring, rash, indentations and infection.

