#### Individual Subject Success Criteria

Individual subject success criteria is defined as a 30% or greater decrease in self-reported VAS pain rating at study endpoint relative to baseline.

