## SECONDARY EVALUATIONS

The following secondary evaluations will be performed in support of the primary efficacy evaluation:

- TOST analysis of the difference in the mean change in VAS levels from baseline to endpoint between the dual-diode and red only diode treatment administration groups.
- Descriptive analysis of the change in mean VAS ratings across all study evaluation points (baseline, endpoint, 24 hours and 48 hours post-procedure).
- Analysis of change in linear ROM measurements across study evaluation points.
- Descriptive analysis of categorical subject satisfaction with study outcome ratings.

Secondary evaluation will be conducted within the dual-diode treatment group and between the dual-diode and red diode only treatment groups.

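### Worsened pain reaches the safety analysis only if someone labels it an adverse event, and the VAS readings already collected are not used to count it

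*Combined protocol and SAP*

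**What the plan says.** **Safety.** Safety Analyses covers all enrolled subjects and consists of "evaluating and comparing frequency and incidence of observed and/or reported adverse events", with a continuity-corrected chi-square test against the red-diode group. The Adverse Events section calls for every potential event, whether the subject reports it or the investigator sees it, to be recorded and then assessed by an independent reviewer for its relation to treatment. Its open-ended list of possible events names "skin irritation, discoloring, rash, indentations and infection". Pain is not on that list, but the adverse event sheet in Appendix C has a pain/discomfort tick box.

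**How events are asked about (Appendix C).** The endpoint form asks whether a potential event was seen by the investigator or reported by the subject. The 24-hour and 48-hour forms, completed at home, ask whether the subject thinks an adverse event is occurring because of the treatment.

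**Use of the VAS.** The individual success criterion is "a 30% or greater decrease in self-reported VAS pain rating at study endpoint relative to baseline". Secondary Evaluations adds "TOST analysis of the difference in the mean change in VAS levels from baseline to endpoint" and "Descriptive analysis of the change in mean VAS ratings across all study evaluation points". No section defines a VAS rise, counts subjects whose VAS rose, or says how a rise relates to adverse event recording.

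**Procedure.** Part of the laser application takes place while the joint is moved, for example: "One minute of pulsed laser is then applied to right shoulder during passive external rotation of the shoulder". A later step is done "during passive left lateral flexion of the cervical spine".

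**The concern.** Subjects enter with a VAS of 50 or more from osteoarthritis, chronic spasm or spine sprain/strain. The protocol's Symptoms section says that this kind of pain gets worse with movement, and the diagnostic criteria for sprain/strain say the same. The procedure moves the neck and shoulders passively. More pain afterwards is therefore a foreseeable unwanted outcome, and in a trial meant to support a pain-relief indication it is one that readers will ask about.

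As planned, the report would give a responder rate, means and an adverse event table. It would not give the number of subjects with more pain after the procedure than before. Such a subject appears in the safety results only if someone judges the increase to be an adverse event. At 24 and 48 hours the form also asks the subject to judge cause, before the independent reviewer whose task that is has seen anything.

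**Working it through.** This point concerns what is counted, so there is no planned power or sample-size figure to reproduce. The sample size of 43 is copied from the reference study. The two reference figures used below do check: 28/43 = 65.1% responders, and 60.2 − 31.2 = 29.0 points mean VAS fall.

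**1. Share of the procedure with passive movement** (Procedure Administration Protocol). Step 4 takes 1 minute and steps 5 and 6 take 2 minutes each, which makes 5 minutes. Steps 7 to 10 on the right and 11 to 14 on the left take 1 minute each, which makes 8 minutes. The total is 13 minutes, and 8 of the 13 involve passive rotation, adduction, lateral flexion or range of motion.

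**2. What the responder endpoint distinguishes.** Take a baseline of 60 (illustrative):
- 60 to 45: a fall of 15/60 = 25%, non-responder.
- 60 to 60: no change, non-responder.
- 60 to 90: a rise of 30/60 = 50%, non-responder.

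All three are counted alike.

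**3. How many subjects can sit in that category in a successful trial.**
- 60% floor (Overall Study Success Criteria): 0.60 × 43 = 25.8, so 26 responders are needed (26/43 = 60.5%). Up to 43 − 26 = 17 subjects (39.5%) may be non-responders.
- Confidence-interval rule (Primary Efficacy Outcome Statistical Evaluation), taking a margin of 5 percentage points, a Wald 90% interval and 28/43 in the reference group: the smallest passing count is 33/43 = 76.7%, where the lower limit is −4.3 points. That still leaves 43 − 33 = 10 non-responders.

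**4. What the mean shows.** If k of 43 subjects rise by w points instead of not changing, the mean fall shrinks by k × w / 43. Starting from the reference fall of 29.0, with k and w assumed:

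| k (of 43) | w | Shift | Mean fall |
|---|---|---|---|
| 2 (4.7%) | 10 | 0.47 | 28.5 |
| 4 (9.3%) | 20 | 1.86 | 27.1 |
| 6 (14.0%) | 20 | 2.79 | 26.2 |
| 6 (14.0%) | 30 | 4.19 | 24.8 |

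Each of these means would still be read as clear benefit.

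**5. What the other planned outputs show.** Satisfaction is tabulated by category, but the lowest category fits an unchanged subject as well as a worsened one. On the home forms, a subject whose pain has risen but who blames the underlying condition can truthfully answer no to the adverse event question.

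**The case against.** A reader might infer that worsened pain is never counted as a safety outcome, or that harm in a minority would be invisible. The documents do not support that. The Adverse Events section covers any potential event, and its list is expressly not exhaustive, so leaving pain off it excludes nothing. Events are asked about at endpoint, 24 hours and 48 hours. The event sheet has a pain/discomfort box, severity grades and free text, and whatever is recorded there enters the safety analysis. At endpoint the question does not depend on attribution, and the VAS and event question belong to the same evaluation at the site. The home forms, VAS marks included, go back to the site. Subjects who worsen also count against the responder rate, and satisfaction by category may reflect some of them.

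Nor do the documents show that the procedure makes pain worse. The protocol describes it as identical to that of the reference study, which reported no adverse events. There is no concurrent control, and subjects agree to go without analgesics and other therapies through 48 hours, so a later rise need not come from the laser session. Treating every VAS rise as an adverse event, or sending each one to the independent reviewer, would mix measurement noise with events.

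All of that stands, and it limits the point. It does not close the gap: the existing route depends on unblinded judgement and, at home, on the subject's view of cause, while a reading taken from every subject for another purpose is not used. Counts could be produced after the fact, but the size of rise would then be chosen with the data in view.

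**Conclusion.** The point holds in limited form. Worsened neck or shoulder pain is countable under the plan, but only through someone's decision to call it an adverse event, and on the 24-hour and 48-hour forms only if the subject attributes it to treatment. The planned VAS summaries cannot fill in, because they do not separate unchanged from worse: up to 17 of 43 subjects (10 of 43 under the confidence-interval rule) may be non-responders of unknown direction, and 4 of 43 rising by 20 points moves a 29.0-point mean fall only to 27.1.

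The number and size of rises in that example are assumptions; the documents give no rate of worsening. The 29.0 is borrowed from the reference study. The point affects what the trial can report on safety. It does not affect the primary analysis or the sample size. The difference between the event list in the Adverse Events section and the tick boxes in Appendix C is clerical and carries no weight here.

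**What to change.** Add one descriptive table to Safety Analyses. For endpoint, 24 hours and 48 hours, report for the dual-diode subjects:
- the number and percentage with any VAS rise from baseline;
- the number and percentage with a rise of at least a pre-specified absolute amount, which the sponsor sets and justifies before the data are seen;
- the full distribution of individual change, as a listing or cumulative plot.

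An absolute amount is preferable to a 30% rise mirroring the success criterion: 100/1.3 = 76.9, so a 30% rise cannot occur from a baseline above about 76.9. Use observed readings with the number observed at each time point, not carried-forward values.

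Show the same for the red-diode group where individual data exist. They may be incomplete after endpoint: the published rescue-medication table for that study has 35 of the 43 active subjects at 24 and 48 hours.

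Place the counts beside the adverse event table, and state that a VAS rise is not by itself classified as an adverse event or automatically forwarded for review.

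The cost is one extra table from data already collected. Its drawback is that some rises will reflect natural fluctuation or withheld analgesics, and a footnote should say so.

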### Study Endpoints

Prior to treatment, a pain rating was recorded for each subject using a 100-point visual analog scale (VAS) where 0 represents no pain and 100 represents worst pain imaginable. Linear range of motion (ROM) was performed to assess patient mobility in the neck-shoulder region using a universal inclinometer. Shoulder ROM was measured from a seated passive abduction. The relaxed position parallel to the side of the body through full extension above head and maximum movement is 180 degrees. Lateral neck ROM was measured in a supine position,

from anatomical position to lateral face over shoulder and maximum movement is 90 degrees. To determine mobility, motion proceeded until it was impeded by pain, muscle restriction, mechanical change, or the normal motion was unimpaired, at which point the degree of range achieved was measured and recorded. Patients were evaluated prior to treatment, immediately post-treatment and after 24 and 48 hours. Immediately following treatment, VAS and ROM assessments were repeated and subjects provided treatment satisfaction rating and perceived treatment group allocation.

Following treatment, subjects were asked to assess their level of treatment satisfaction with respect to their overall improvement in pain using a scale ranging from Very Satisfied to Not at All Satisfied and were asked to indicate their perceived group assignment. Subjects were also evaluated 24 and 48 hours after treatment. At that time, they were asked to grade their physical activity from Very Physically Active to Not at All Physically Active and provide a list of all specific physical activities they performed during the previous 24- and 48-hour periods. Participants were asked to refrain from using any analgesic medications until the 48-hour post-procedure evaluation was completed and to report the use of and rescue medications.

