Among the enrolled subjects, 76 participated in the satisfaction survey. Among subjects in the LLLT group, 89.5% reported being Very Satisfied or Somewhat Satisfied compared to 34.3% of subjects in the sham group ( $p < 0.0001$ ). Conversely, 23.7% of sham-treated subjects were Not Very Satisfied or Not at All Satisfied compared to 2.6% of LLLT-treated subjects.

There were no reports of adverse events.

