### **SUBJECT GROUP**

There will be a single subject group in this study. All subjects will receive the active study procedure with the red and violet diodes of the Erchonia® EVRL emitted simultaneously.

Comparative subject data for the red diode alone procedure administration will be taken from the 2001 study whose results supported FDA market clearance for K050672.

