#### Sample Size

There will be 43 qualified subjects enrolled in this study.

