**Please mark any of the boxes below that are applicable:**  
The subject's reported adverse event can be categorized as follows:

	skin irritation
	itching
	discoloring
	rash/hives
	indentations
	pain/discomfort
	other: _____

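### The planned test of adverse event rates against the historical red-diode group cannot separate a device effect from how events were collected, because the reference trial's collection method is not described

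*Combined protocol and SAP*

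**What the plan says.** The Safety Analyses section bases safety on all enrolled subjects and plans "evaluating and comparing frequency and incidence of observed and/or reported adverse events between dual-diode and red diode only procedure groups". It then adds a formal test: "A chi-square test with a continuity correction will be performed to compare the percentage of subjects who had adverse events between the two subject groups".

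The red-diode group is not enrolled in this trial. Under Subject Group, "Comparative subject data for the red diode alone procedure administration will be taken from the 2001 study". Under Sample Size, "There will be 43 qualified subjects enrolled in this study", and the published reference trial also treated 43 subjects with the active laser.

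In the new trial an adverse events evaluation is listed among the outcome assessments at study endpoint and again at 24 and 48 hours. The case report forms in Appendix C carry a yes/no item at each of the three times. The investigator completes the endpoint item, and the subject completes the other two at home.

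For the reference trial, the Study Endpoints section of the reproduced publication says that immediately after treatment "VAS and ROM assessments were repeated and subjects provided treatment satisfaction rating and perceived treatment group allocation". For 24 and 48 hours it describes grading of physical activity, a list of activities and reporting of rescue medication. The publication's whole safety result is one sentence: "There were no reports of adverse events".

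**The concern.** A test of two adverse event percentages is interpretable only if both groups had their events counted in the same way. In a concurrent trial that follows from using the same forms. Here the two percentages come from separate studies, and nothing in the protocol says how red-diode events were collected or allows for a difference in collection.

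Two misreadings are possible. If the new forms bring out minor events that the reference trial did not record, the excess would look like a harm of adding violet light. If few events occur, a non-significant p-value could be read as showing that the two modes are equally safe. The results are intended to support a 510(k) submission, so the sponsor has reason to avoid both.

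**Working it through.** **1. Collection, side by side**

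| | Dual-diode (this trial) | Red diode (reference trial, as published) |
|---|---|---|
| Right after treatment | Investigator ticks whether an event was observed or reported | Pain score, range of motion, satisfaction, perceived allocation; no adverse event item described |
| 24 h and 48 h | Subject answers yes/no on a home form whether an event from the treatment is being experienced | Activity grade and list, rescue medication; no adverse event item described |
| Result | To be collected | No events reported |

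The Study Endpoints section of the publication is not a complete list. It does not name the pain score among the 24 and 48 hour items, yet the publication's results report pain scores at both times. Absence from that list therefore leaves the collection method unknown. It does not show that nothing was asked.

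**2. What the planned test can do**

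Inputs: 43 dual-diode subjects (Sample Size); 43 red-diode subjects with no reported event (publication, Results). The plan gives no significance level for the safety test, so two-sided 0.05 is assumed. The protocol gives no power or event rate for this comparison, so there is no stated figure to reproduce.

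Let x be the number of dual-diode subjects with an event, against 0 of 43. The continuity-corrected statistic is

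chi-square = N(|ad − bc| − N/2)² / (n1 · n0 · m · (N − m)),

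with N = 86, n1 = n0 = 43, m = x and |ad − bc| = 43x. This reduces to 86(x − 1)² / (x(86 − x)).

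- x = 5: 86 × 16 / (5 × 81) = 1376 / 405 = 3.40, p = 0.065
- x = 6: 86 × 25 / (6 × 80) = 2150 / 480 = 4.48, p = 0.034

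The threshold is 6 of 43 (14.0%). Fisher's exact test has the same threshold (5: p = 0.055; 6: p = 0.026), so changing the test does not change the picture. If the reference denominator were the 35 active-laser subjects in the publication's 24 and 48 hour rescue-medication table, the threshold would be 7 (p = 0.035).

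**3. How often the threshold would be reached**

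The reference count is already known, so the only random quantity is x, taken as binomial with n = 43 and true rate p. The rates are assumptions, shown as a range.

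| Assumed true dual-diode rate | P(x ≥ 6) |
|---|---|
| 2% | 0.02% |
| 5% | 1.9% |
| 10% | 25.7% |

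These probabilities hold whatever share of events the reference trial captured, because its count is fixed at zero.

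**The case against.** The strongest reply is that the case rests on silence in a journal article. That is right as far as it goes. A reader might infer that reference events were only volunteered, or that any difference must partly measure ascertainment. The documents support neither, because the 2001 forms are unseen and the published list has at least one known gap.

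The new trial's collection is also easy to overstate:

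- The endpoint item is an investigator tick and not a question put to the subject.
- The home items ask only about current events that the subject attributes to the treatment.
- The category list, introduced by "The subject's reported adverse event can be categorized as follows", is on a sheet completed after an event is raised, so it classifies events and does not elicit them.
- Events are "subsequently evaluated by a suitably qualified independent reviewer for determination of relationship to the study treatment", but the tested count is all observed or reported events, so that review does not alter it.
- Blinding in the reference trial did not stop subjects from reporting or attributing events.

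A further reply is that events should be rare. The publication reports none, and the Adverse Events section expects none. No section supports true rates of 10% or more, so a false signal is improbable. Nor does the plan state a hypothesis or a claim of equal safety.

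The statement under Evaluation Time Point that the endpoint evaluation matches the reference study does not settle the matter. It concerns timing and does not mention adverse events.

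What survives these replies is narrower. The plan commits to a p-value whose meaning depends on comparable collection, and nothing in the documents establishes that.

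**Conclusion.** The concern holds in this limited form: comparable adverse event collection is undocumented, so a difference in either direction could not be separated from how events were collected. The documents do not show that collection actually differed, nor by how much.

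In practice the test is close to inert. It can reject only at 6 or more events among 43. At assumed true rates of 5% or less the chance of that is 1.9% or less. It rises to 25.7% at 10%, a rate the documents do not suggest. With so little chance of rejecting at low rates, a non-significant result would be no evidence of equal safety. A significant one could not be assigned to the violet diode.

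This rests on a reference count of 0 of 43 and a two-sided 0.05 level. Severity is low to moderate. The primary endpoint is unaffected.

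**What to change.** In Safety Analyses:

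- Drop the chi-square test.
- Report adverse event incidence for all enrolled dual-diode subjects with an exact 95% confidence interval, overall and by category, severity and relationship. For scale, 0 of 43 would give an upper limit of 1 − 0.025^(1/43) = 8.2%.
- Present the reference trial's absence of reported events descriptively, and state that its method of collecting adverse events is not described.
- Keep a side-by-side comparison only if the 2001 case report forms show that the same events were asked for at the same time points.

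The cost is a change of wording, with no new data or subjects. The sponsor gives up the formal between-group safety p-value. Keeping the test but labelling it exploratory would be a weaker alternative, because the p-value would still lack a clear meaning without the 2001 forms.
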